1.4. Risk Management

Subjects will be monitored in the Clinical Research Unit (CRU) for at least 12 hours after dosing with the study treatment and monitored. Subjects will be allowed liquid and solid oral intake ad libitum during the study with a minimum of 100 mL of fluid consumed for every 300 mL of urine output. Subjects with abnormal serum potassium levels at screening will be excluded from the study. Blood pressure and heart rate will be monitored during and after the injections.

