3. INVESTIGATIONAL PLAN

3.1. Overall Study Design and Plan

This is an open-label, single-center, single-dose, randomized, two-way (two-period) crossover study in healthy volunteers. Each Subject will complete Screening, Baseline, Treatment, and Follow-up Phases.

The Screening Phase will be conducted on an outpatient basis between 14 and 3 days prior to the Baseline visit. Subjects will be instructed to maintain a < 2-gram sodium diet and abstain from caffeine-containing products within 2 days prior to admission to the CRU. On arrival to the CRU (Day 0), baseline and final qualification assessments will be performed.

The Treatment Phase will be comprised of two crossover periods separated by a 3 ± 1 day washout period. During each CRU admission and through the washout period, Subjects will continue a < 2-gram sodium diet and abstain from caffeine-containing products. Subjects will be randomly assigned in a 1:1 ratio to 1 of 2 treatment sequences to receive IV furosemide and SC SCP-111 in the abdomen in Crossover Periods (ie, IV followed by SC or vice versa). Blood samples will be collected to measure plasma furosemide concentrations at pre-dose and for 12 hours post-dose. Prior to dosing in each Treatment Phase, subjects will void their bladder completely and urine will be collected starting after the injection through 12 hours post injection to determine total urine output and urinary sodium and potassium excretion. Assessment of injection site pain will be conducted for IV and SC administration using an 11-point pain scale. Photographs of the injection site will be performed prior to the IV and SC injection (baseline) and 4 hours post IV administration and 6 hours post SC administration. In addition, a photograph will be taken of the IV and SC injection site for any AE (i.e., erythema, edema, pruritus, bruising) that occurs at the site at the time of the event. Subjects will remain domiciled in the CRU for each Crossover Period during the Treatment Phase through 12 hours after administration of study drug. After final assessments are performed, Subjects may be discharged from the CRU if safety parameters are acceptable to the Investigator.

The Follow-up Phase will occur 24-48 hours (Day 5 ± 1) after discharge from the CRU following Crossover Period 2, completing Subjects' study participation.

[figure not shown]

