3.2.2. Pharmacodynamic Endpoints

Urine will be collected from spontaneous voids in 1-hour increments for the first 8 hours and in 2-hour increments up to 12 hours post-dose. Total urine output for each time period ((0-1), (1-2), (2-3), (3-4), (4-5), (5-6), (6-7), (7-8), (8-10) and (10-12) hours after initiation of dosing) will be recorded. The 6-hour, 8-hour and 12-hour urine output for IV furosemide and SC SCP-111 will be compared using appropriate statistical tests. In addition, an aliquot of urine will be used from each time period ((0-1), (1-2), (2-3), (3-4), (4-5), (5-6), (6-7), (7-8), (8-10) and (10-12) hours after initiation of dosing) for quantification of urinary sodium and urinary potassium. The 6-hour, 8-hour and 12-hour urinary sodium and potassium excretion will be determined and compared for IV furosemide and SC SCP-111 using appropriate statistical tests.

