6.2.1.2. Baseline Assessment (Day 0)

Subjects will be admitted to the CRU on Day 0 (the day of study drug administration) for Baseline assessment and procedures. Low sodium diet (< 2 gram per day) and fluid intake ad libitum consisting of water, juice and caffeine free beverages are permitted while domiciled in the CRU. Subjects will be monitored during the study to ensure a minimum of 100 mL of fluid consumed for every 300 mL of urine output.

The following assessments will be completed at Baseline upon CRU admission:

1. Eligibility re-review
2. Limited physical examination as described in Section 6.2.2.1
3. Prior medication assessment
 - Time and date of last dose of oral loop diuretic (if receiving)
4. Weight measurement
5. Temperature
6. Blood pressure
7. Heart rate
8. Clinical laboratory tests as described in Section 6.2.2.3
9. Alcohol breath test
10. Urine drug screen
11. Urine pregnancy test as applicable
12. Randomization to treatment sequence
13. Photograph of Injection Site as described in Section 6.2.2.8

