6.2.1.5. Pre-Period 2 Assessment (Day 3 ± 1)

Subjects will present to the CRU on Day 3 ±1 for Pre-Period 2 assessment and procedures. Low sodium diet and fluid intake ad libitum consisting of water, juice and caffeine free beverages are permitted while domiciled in the CRU. Subjects will be monitored during the study to ensure a minimum of 100 mL of fluid consumed for every 300 mL of urine output.

The following assessments will be completed at the Pre-period 2 assessment upon CRU admission:

1. Limited physical examination as described in Section 6.2.2.1
2. Concomitant medication assessment

- a. Time and date of last dose of oral loop diuretic (if receiving)
3. Weight measurement
4. Temperature
5. Blood pressure
6. Heart rate
7. Clinical laboratory tests as described in Section 6.2.2.3
8. Alcohol breath test
9. Urine drug screen
10. Urine pregnancy test as applicable
11. Adverse events

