- ⁴ Clinical labs include sodium, potassium, calcium, chloride, magnesium, carbon dioxide, blood urea nitrogen (BUN), serum creatinine, glucose, hemoglobin, and hematocrit. Post-dose clinical labs on Day 0 and Day 3 should be performed 12 hours after the study drug is administered.
- ⁵ Pregnancy test for females of child-bearing potential.
- ⁶ Intravenous furosemide is administered as 40 mg over 1 to 2 minutes followed by a second dose of 40 mg over 1 to 2 minutes, 2 hours apart by IV injection. SCP-111 is administered as a single, 80-mg dose by subcutaneous injection via an autoinjector.
- ⁷ Pharmacokinetic sampling per instructions in 6.2.2.6
- ⁸ Subjects will be instructed to void immediately before dosing (pre-dose urine) and this sample will be discarded. Urine from spontaneous voids during post-dose phases will be collected and pooled, measured, recorded for time periods (0-1), (1-2), (2-3), (3-4), (4-5), (5-6), (6-7), (7-8), (8-10) and (10-12) hours after initiation of dosing. Urine from each collection period must be collected in a single vessel and refrigerated until the end of the collection period. Urinary sodium and urinary potassium concentrations for each collection interval over the 12-hour urine collection period will be analyzed by standard lab biochemistry test. Total urine output volume will be documented for each collection period.
- ⁹ Low sodium snacks and meals as well as water, juice, and caffeine free beverages will be allowed ad libitum, and the amount measured and recorded over the post-dose phases. Subjects will be monitored to ensure a minimum of 100 mL of fluid consumed for every 300 mL of urine output.
- ¹⁰ Assessment of injection site pain for IV administration performed pre-dose after IV needle placement, immediately after 1st dose and 15 and 30 minutes after 1st dose, immediately after 2nd dose and 15 and 30 minutes and 4 and 10 hours after the 2nd dose. For SC administration, injection site pain conducted pre-dose, immediately after dose and 15 and 30 minutes and 6 and 12 hours after dose.
- ¹¹ Photographs of the injection site will be performed prior to the IV and SC injection (baseline) and 4 hours post IV administration or 6 hours post SC administration. In addition, a photograph will be taken of the IV and SC injection site for any AE (i.e., erythema, edema, pruritus, bruising) that occurs at the site at the time of the event.

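### Food is unstandardised in the two CRU stays, which adds avoidable within-subject noise to the secondary urinary sodium and potassium comparisons

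*Protocol*

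**What the plan says.** Protocol 1.4 sets the general rule: "Subjects will be allowed liquid and solid oral intake ad libitum during the study". To this it attaches a floor on drinking, tied to diuresis. Appendix 1, footnote 9, repeats the rule for the post-dose phases: "Low sodium snacks and meals as well as water, juice, and caffeine free beverages will be allowed ad libitum". The same footnote requires the amounts to be measured and recorded. The Period 1 text (6.2.1.2) reads "Low sodium diet (< 2 gram per day) and fluid intake ad libitum consisting of water, juice and caffeine free beverages are permitted", and the Period 2 text (6.2.1.5) reads "Low sodium diet and fluid intake ad libitum consisting of water, juice and caffeine free beverages are permitted while domiciled in the CRU".

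Several controls are common to both stays. Protocol 3.1 says of each admission and the washout that "Subjects will continue a < 2-gram sodium diet and abstain from caffeine-containing products". Protocol 6.2.2.9 adds abstinence from alcohol over the same span, starting two days before Baseline. The minimum-fluid rule and the permitted drinks are the same in both periods.

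On the endpoints, protocol 3.2.2 states: "The 6-hour, 8-hour and 12-hour urinary sodium and potassium excretion will be determined and compared for IV furosemide and SC SCP-111". Protocol 8.5 describes this comparison as descriptive. SAP 9.2 goes further, with a repeated-measures mixed model, 95% confidence intervals for SC versus IV and p-values. SAP section 9 gives the SAP precedence over the protocol.

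**The concern.** A crossover is efficient because each subject is their own control. That works best when the external drivers of the outcome are alike in the two periods. For urinary sodium and potassium, what the subject eats, how much and when are such drivers, and the plan leaves them to the subject's choice in each stay. Sodium has a ceiling but no target. Potassium has neither, and juice is allowed. Meal timing is also free, although two of the three accumulation windows close at 6 and 8 hours, so a meal taken earlier in one period than in the other can shift excretion across a window boundary.

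At stake is the precision of the secondary sodium and potassium contrasts, and how readily a modest SC-IV difference in them can be read as a drug effect.

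**Working it through.** **1. The plan's own figure.** The only sample-size statement is for AUCinf (protocol 8.1, SAP Sample Size): 18 completers, 21 enrolled, at least 90% power. Halving the 31.6% total CV gives an intra-subject CV of 15.8%. Then s_w = sqrt(ln(1 + 0.158²)) = 0.157 and SE = s_w × sqrt(2/18) = 0.052, with 16 degrees of freedom. Exact power of the two one-sided tests within 80-125% is 93.2% at a true ratio of 0.95 and 93.8% at 1.05, so the stated figure is reproduced. It rests on plasma AUC variability; nothing in the present argument enters it. No sample size, margin or variance is given for any urine endpoint.

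**2. What is and is not matched between the two stays.**

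| Item | Rule | Matched between periods? |
|---|---|---|
| Dietary sodium | Below 2 g per day (3.1, 6.2.1.2) | Ceiling only |
| Dietary potassium | None stated | No |
| Menu and meal times | None stated | No |
| Fluid volume | Minimum tied to urine output (1.4, 6.2.1.2, 6.2.1.5) | Same floor, no ceiling |
| Types of drink | Water, juice, caffeine free (6.2.1.2, 6.2.1.5) | Yes |
| Caffeine and alcohol | Excluded (6.2.2.9) | Yes |
| Recording of intake | Amount measured post-dose (6.2.1.3.3, 6.2.1.6.3, Appendix 1) | Yes, but no SAP summary |

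**3. How it enters the analysis.** For one subject, the SC-IV difference in excretion is the treatment effect, plus f × (intake in the SC period − intake in the IV period), plus remaining error. Here f is the fraction of an intake difference that reaches the urine within the window. If the intake difference is independent of the remaining error,

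Var(difference) = base variance + f² × Var(intake difference).

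The model in SAP 9.2 has treatment, time, their interaction and a random subject effect. A subject's intake differs by period, so the random subject effect does not absorb it and it stays in the error.

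**4. Size.** The documents give neither the base variance, nor f, nor the intake variance, so the loss cannot be computed. As an assumption only, let r be the added variance as a share of the base. The interval is then sqrt(1 + r) times as wide, and matching the precision that 18 subjects would have without the noise takes 18 × (1 + r) subjects, rounded up.

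| Assumed r | Interval width | Subjects for equal precision |
|---|---|---|
| 10% | × 1.05 | 20 |
| 25% | × 1.12 | 23 |
| 50% | × 1.22 | 27 |
| 100% | × 1.41 | 36 |

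The table shows what the mechanism does if r takes these values. It is not an estimate for this trial, and it is not the gain to expect from a fixed menu, which would remove only part of r.

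**The case against.** The strongest reply is that intake is already constrained, and alike in kind, in both stays: a common sodium ceiling with a two-day run-in, no caffeine or alcohol, a common fluid floor, the same permitted drinks, and recorded amounts. The endpoints are secondary, the stated objective is to describe, and no pharmacodynamic success criterion depends on them. A served menu also does not guarantee equal consumption. All of this stands. It limits the point to an inexpensive improvement but does not remove it, since none of these controls fixes the amount or timing of sodium and potassium eaten.

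Three stronger readings are tempting, and the documents do not support them.

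- A reader might infer that the comparison is biased, because the study is open-label and intake responds to diuresis. In a randomised crossover, intake differences unrelated to treatment are noise. Intake that rises with diuresis follows from treatment and is partly required by the fluid rule. The documents give no mechanism by which knowing the route would change what subjects eat. Bias is possible but not shown.
- A reader might turn the ceiling into a between-period sodium difference: 2000 mg / 22.99 = 87 mEq. That is a 24-hour limit set against a 12-hour collection, and it needs no sodium at all in one stay and the full allowance in the other. It is an outer bound, not a realistic difference.
- A reader might extend the argument to urine volume and put a figure on the lost precision from assumed fluid intakes. The change proposed here leaves fluid volume free, so such a figure would not measure what the change recovers.

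**Conclusion.** The point holds as a low-cost improvement. Unstandardised solid food adds avoidable within-subject noise to the SC-IV comparisons of urinary sodium and potassium excretion. The consequence is wider intervals than necessary by an amount that the documents do not allow one to compute. The conclusion rests on two assumptions: that dietary sodium and potassium taken in or shortly before a window affect excretion within it, and that free choice leads subjects to eat differently in the two stays. The pharmacodynamic analysis is not invalid as planned, and the argument does not touch the primary AUC comparison or its sample size.

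**What to change.** In protocol 1.4, 6.2.1.2, 6.2.1.5 and Appendix 1 footnote 9, replace free choice of solid food by one low-sodium menu with the same sodium and potassium content, served at the same hours after dosing in both periods. Keep recording the amount eaten, as already planned, because a common menu narrows intake differences but does not abolish them. Leave the fluid rule unchanged.

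In the SAP, add a table of recorded food and fluid intake by treatment and period, so that any imbalance can be seen beside the urine results. Do not enter post-dose intake as a covariate in the 9.2 model: required fluid rises with urine output, so intake is itself affected by treatment, and adjusting for it could distort the contrast.

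The cost is protocol wording, some menu planning, one added table and less choice for subjects. The plan already provides for low-sodium meals and for recording amounts during the stays. If the menu cannot be changed, the intake table alone is still worth having.

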2. STUDY OBJECTIVES

The primary objective of the study is:

- 1.) To estimate the bioavailability of SCP-111 80 mg/1 mL administered as a subcutaneous injection via an autoinjector compared with an equivalent dose of furosemide administered as two 40 mg intravenous injections over one to two minutes, two hours apart.

The secondary objectives of the study are:

- 1.) To describe the pharmacokinetics and pharmacodynamics of SCP-111 80 mg/1 mL administered as a subcutaneous injection via an autoinjector.
- 2.) To describe the safety and tolerability of SCP-111 80 mg/1 mL administered as a subcutaneous injection via an autoinjector.

3. INVESTIGATIONAL PLAN

3.1. Overall Study Design and Plan

This is an open-label, single-center, single-dose, randomized, two-way (two-period) crossover study in healthy volunteers. Each Subject will complete Screening, Baseline, Treatment, and Follow-up Phases.

The Screening Phase will be conducted on an outpatient basis between 14 and 3 days prior to the Baseline visit. Subjects will be instructed to maintain a < 2-gram sodium diet and abstain from caffeine-containing products within 2 days prior to admission to the CRU. On arrival to the CRU (Day 0), baseline and final qualification assessments will be performed.

The Treatment Phase will be comprised of two crossover periods separated by a 3 ± 1 day washout period. During each CRU admission and through the washout period, Subjects will continue a < 2-gram sodium diet and abstain from caffeine-containing products. Subjects will be randomly assigned in a 1:1 ratio to 1 of 2 treatment sequences to receive IV furosemide and SC SCP-111 in the abdomen in Crossover Periods (ie, IV followed by SC or vice versa). Blood samples will be collected to measure plasma furosemide concentrations at pre-dose and for 12 hours post-dose. Prior to dosing in each Treatment Phase, subjects will void their bladder completely and urine will be collected starting after the injection through 12 hours post injection to determine total urine output and urinary sodium and potassium excretion. Assessment of injection site pain will be conducted for IV and SC administration using an 11-point pain scale. Photographs of the injection site will be performed prior to the IV and SC injection (baseline) and 4 hours post IV administration and 6 hours post SC administration. In addition, a photograph will be taken of the IV and SC injection site for any AE (i.e., erythema, edema, pruritus, bruising) that occurs at the site at the time of the event. Subjects will remain domiciled in the CRU for each Crossover Period during the Treatment Phase through 12 hours after administration of study drug. After final assessments are performed, Subjects may be discharged from the CRU if safety parameters are acceptable to the Investigator.

The Follow-up Phase will occur 24-48 hours (Day 5 ± 1) after discharge from the CRU following Crossover Period 2, completing Subjects' study participation.

[figure not shown]
3.1.1. Study Treatment

Study Drugs:

- **Furosemide Injection 10 mg/mL, USP:** Hospira, furosemide injection, solution 10 mg/mL (NDA 018667), administered intravenously 40 mg over 1 to 2 minutes by IV injection followed by a second dose of 40 mg administered over 1-2 minutes, 2 hours later (reference treatment).
- **SCP-111 (furosemide injection 80 mg/1 mL):** SCP-111 80 mg/1 mL for subcutaneous administration, (total dose = 80 mg dose) administered as a subcutaneous injection (test treatment) via an autoinjector.

Study drug will be administered at time zero (0) for the purpose of documenting drug administration, PK plasma sampling, urine collection, and AE monitoring according to the Time and Event Schedule. Serial sampling of venous blood for quantitation of furosemide in plasma will be collected over 12 hours according to the schedule of procedures. Urine will be collected from spontaneous voids in 1-hour increments for the first 8 hours and in 2-hour increments up to 12 hours post-dose, for the purpose of determining the total urine volume and urinary sodium and potassium concentration over 12 hours. Plasma samples will be processed and stored according to the instructions in the protocol and assayed using validated bioanalytical methods.

3.1.2. Study Schematic

^aSCP-111 80 mg SC administered via an autoinjector

^bFurosemide IV administered as two, 40 mg doses (over 2 minutes) 2 hours apart (80 mg total dose)

CRU=clinical research unit; h=hour; IV=intravenous; min=minute; PK= pharmacokinetics; PD=pharmacodynamics; SC=subcutaneous

^cFollow-up visit should occur 24-48 hours after discharge from CRU for Crossover Period 2

3.2. Endpoints

3.2.1. Pharmacokinetic Endpoints

Individual pharmacokinetic parameters for furosemide will be summarized with descriptive statistics. Pharmacokinetic parameters including the maximum observed plasma concentration (C_{max}), the area under the plasma concentration versus time curve from time 0 (pre-dose) to the last quantifiable time point (AUC_{last}), the AUC from time 0 (pre-dose) to time infinity (AUC_{inf}), the time to C_{max} (T_{max}), the terminal phase elimination rate constant (λ_z), the terminal elimination half-life ($t_{1/2}$) for both SC SCP-111 (test) and IV furosemide (reference), the apparent systemic clearance (CL/F) for SC SCP-111 and systemic clearance (CL) for IV furosemide, the apparent systemic volume of distribution (V_z/F) for SC SCP-111 and systemic volume of distribution (V) for IV furosemide will be calculated using noncompartmental analysis. Bioavailability of SC SCP-111 will be determined based on the logarithmic transformation of the geometric mean ratios of AUC_{last} and AUC_{inf} of IV furosemide (reference) and SC SCP-111 (test) and 90% confidence intervals will be calculated. Compartmental modeling of the pharmacokinetic data may be conducted.

3.2.2. Pharmacodynamic Endpoints

Urine will be collected from spontaneous voids in 1-hour increments for the first 8 hours and in 2-hour increments up to 12 hours post-dose. Total urine output for each time period ((0-1), (1-2), (2-3), (3-4), (4-5), (5-6), (6-7), (7-8), (8-10) and (10-12) hours after initiation of dosing) will be recorded. The 6-hour, 8-hour and 12-hour urine output for IV furosemide and SC SCP-111 will be compared using appropriate statistical tests. In addition, an aliquot of urine will be used from each time period ((0-1), (1-2), (2-3), (3-4), (4-5), (5-6), (6-7), (7-8), (8-10) and (10-12) hours after initiation of dosing) for quantification of urinary sodium and urinary potassium. The 6-hour, 8-hour and 12-hour urinary sodium and potassium excretion will be determined and compared for IV furosemide and SC SCP-111 using appropriate statistical tests.

3.2.3. Safety and Tolerability Endpoints

3.2.3.1. Safety

Incidence of Adverse Events (AEs) and Serious Adverse Events (SAEs) grouped by body system for IV furosemide (reference) and SC SCP-111 (test).

Changes in pre-dose clinical labs, blood pressure and heart rate through CRU discharge will be summarized for IV furosemide (reference) and SC SCP-111 (test).

3.2.3.2. Injection Site Pain

Injection site pain will be assessed using an 11-point scale where 0 is equivalent to no pain and 10 is equivalent to the worst possible pain for IV administration and for SC administration. Pain requiring treatment, withdrawal from the study or discontinuation of study drug will also be recorded as an adverse event (AE) ([Appendix 2](#)).

